4.3 EARLY TERMINATION/SAFETY FOLLOW-UP VISIT

An early termination visit is required for any subjects who permanently discontinue study drug early for any reason including disease progression. Each subject should be followed for 30 (± 7) days after his or her last dose of study drug (ie, the "safety follow-up visit") to monitor for resolution or progression of AEs (see [Section 6.2.6](#)) and to document the occurrence of any new events, unless the subject receives a new anticancer therapy within this timeframe. Subjects who withdraw consent should still be encouraged to complete the safety follow-up assessments, but these assessments cannot be mandated once consent is withdrawn. The Schedule of Assessments ([Appendix 4](#)) describes the procedures required for the safety follow-up.

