3.0 STUDY DESIGN

3.1 DESCRIPTION OF STUDY

This study is a multicenter and open-label study. Twenty subjects, 10 relapsed and 10 refractory, will be enrolled and will take 100 mg of *acalabrutinib* BID. The study will be conducted at approximately 9 sites in up to 4 countries.

Relapsed subjects will be defined as subjects who have had a PR or better ([Cheson 2014](#) or [Cheson 2007](#) criteria) from the previous anticancer therapy and now have progressed. Refractory subjects will be defined as subjects whose best response to the previous anticancer therapy was SD or did not respond to therapy.

Treatment with *acalabrutinib* may be continued for > 28 days until disease progression or an unacceptable drug-related toxicity occurs. Tumor assessments will be performed at 8- to 12-week intervals during the trial. Dose modification provisions are provided in

[Section 3.5.5](#). Note: temporary withholding of study drug for as little as 7 days can cause a transient worsening of disease and/or of constitutional symptoms. Refer to [Section 3.8](#) for more information on assessing disease progression under these circumstances. All subjects who discontinue study drug will have a safety follow-up visit 30 (± 7) days after the last dose of study drug unless they have started another cancer therapy within that timeframe.

All subjects will have hematology, chemistry, and urinalysis safety panels done at screening. Once dosing commences (Day 1), all subjects will be evaluated for safety, including serum chemistry and hematology, once weekly for the first 4 weeks, every 2 weeks in Cycle 2 and monthly thereafter. PK/PD testing will be done in Cycle 1 and Cycle 2.

Refer to [Appendix 4](#) for a comprehensive list of study assessments and their timing. Subjects showing clinical benefit and who are tolerating *acalabrutinib* may remain on study through the end of Cycle 12. The end of trial is defined as the point when the last subject enrolled completes the end of Cycle 12 or withdraws for any reason and completes the 30-day follow-up visit (if applicable), whichever occurs first.

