3.4 SELECTION OF STUDY POPULATION

3.4.1 Inclusion Criteria

Eligible subjects will be considered for inclusion in this study if they meet **all** of the following criteria:

1. Men and women ≥ 18 years of age.
2. Eastern Cooperative Oncology Group (ECOG) performance status of ≤ 2 .
3. Pathologically confirmed de novo ABC DLBCL, and subjects **must have** available archival tissue for central pathology review to be eligible.
4. Relapsed or refractory disease, defined as either: 1) recurrence of disease after a CR, or 2) PR, SD, or progressive disease at completion of the treatment regimen preceding entry to the study (residual disease):
 - Subjects must have previously received a standard anthracycline and rituximab-based first-treatment regimen (eg, R-CHOP).
 - Subjects with suspected residual disease after the treatment regimen directly preceding study enrollment must have biopsy demonstration of residual DLBCL.
 - Subjects who have not received HDT/ASCT must be ineligible for HDT/ASCT as defined by meeting any of the following criteria:
 - Age ≥ 70 years
 - Diffuse lung capacity for carbon monoxide (DLCO) $< 50\%$ by PFT
 - Left ventricular ejection fraction (LVEF) $< 50\%$ by ECHO
 - Other organ dysfunction or comorbidities precluding the use of HDT/ASCT on the basis of unacceptable risk of treatment-related morbidity
 - Subject refusal of HDT/ASCT
 - Subjects who are intolerant to anthracycline-based first-line therapy and meet all other eligibility criteria including recurrent or refractory disease are also eligible.
5. Presence of radiographically measurable lymphadenopathy or extranodal lymphoid malignancy (defined as the presence of ≥ 1 lesion that measures ≥ 2.0 cm in the longest dimension and ≥ 1.0 cm in the longest perpendicular dimension as assessed by CT scan).
6. Agreement to use acceptable forms of contraception during the study and for 30 days after the last dose of study drug if sexually active and able to bear or beget children.

7. Agreement to refrain from sperm donation during the study and for 30 days after the last dose of study drug.
8. Willing and able to participate in all required evaluations and procedures in this study protocol including swallowing capsules without difficulty.
9. Ability to understand the purpose and risks of the study and provide signed and dated informed consent and authorization to use protected health information (in accordance with national and local patient privacy regulations).

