6.2.1 Adverse Event Reporting Period

After the signing of the ICF and prior to the first dose of study drug, all SAEs must be reported. After the first dose of study drug, all AEs/SAEs, irrespective of attribution of causality, must be reported.

All adverse events will be reported until 30 days after the last dose of study drug or the start of new anticancer therapy (whichever comes first). After this period, investigators should report serious adverse events or other adverse events of concern that are believed to be related to prior treatment with study drug.

All SAEs that occur during the reporting period should be followed to resolution or until the Investigator assesses the subject as stable or until the subject is lost to follow-up or withdraws consent. Resolution/stable means the subject has returned to baseline state of health or the investigator does not expect any further improvement or worsening of the event.

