Abbreviations: anti-HBc = hepatitis B core antibody; CR = complete remission; ECG = electrocardiogram; ECOG = Eastern Cooperative Oncology Group; ET = early termination; HBsAb = hepatitis B surface antibody; HBsAg = hepatitis B surface antigen; HBV = hepatitis B virus; HCV = hepatitis C virus; Ig = immunoglobulin; IVIG = intravenous immunoglobulins; LTFU = long-term follow-up; mos = months; PCR = polymerase chain reaction; PE = physical exam; QM = every month.

Footnotes for ACE-LY-002 Schedule of Study Activities:

- a. Screening tests should be performed within 21 days before the first administration of study drug, unless otherwise indicated.
- b. Any subjects who have not progressed while receiving study drug treatment, may be eligible to enroll into a long-term follow up study and continue to receive *acalabrutinib*.
- c. An early termination visit will be done for subjects who permanently discontinue study drug early for any reason. A 30-day (\pm 7 days) safety follow-up visit is required when subjects discontinue study drug unless they start another anticancer therapy within that timeframe.
- d. The screening physical examination will include, at a minimum, the general appearance of the subject, height (screening only) and weight, and examination of the skin, eyes, ears, nose, throat, lungs, heart, abdomen, extremities, musculoskeletal system, lymphatic system, and nervous system. Symptom-directed physical exams, including tumor assessments by palpation, are done thereafter.
- e. Vital signs (blood pressure, pulse, respiratory rate, and temperature) will be assessed after the subject has rested in the sitting position.
- f. Subjects should be in supine position and resting for \geq 10 minutes before study-related ECGs.
- g. Women of childbearing potential only. If positive, pregnancy must be ruled out by ultrasound to be eligible.
- h. Cycle 1 Day 1 testing does not need to be repeated if screening hematology was done within 7 days of first dose of study drug. Hematology includes complete blood count with differential and platelet counts.

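### The safety follow-up visit may be held from day 23 after the last dose, although adverse events and concomitant medications are collected to day 30 and no later collection of either is scheduled

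*Protocol*

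**What the plan says.** Protocol Section 4.3: "Each subject should be followed for 30 (± 7) days after his or her last dose of study drug". The stated purpose is to monitor the course of existing AEs and "to document the occurrence of any new events, unless the subject receives a new anticancer therapy within this timeframe". Section 3.1 has the same visit ("All subjects who discontinue study drug will have a safety follow-up visit 30" days, ±7), and so do the synopsis and Appendix 4 footnote c, under which a "safety follow-up visit is required when subjects discontinue study drug unless they start another anticancer therapy within that timeframe".

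The collection periods are worded differently. Section 6.2.1: "All adverse events will be reported until 30 days after the last dose of study drug or the start of new anticancer therapy", with the earlier of the two ending the period. Beyond that point, "investigators should report serious adverse events or other adverse events of concern that are believed to be related to prior treatment with study drug". Section 4.1.4 records concomitant medications until 30 days after the last dose. Neither section gives a tolerance.

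Section 6.2.2 has investigators assess AEs at each evaluation of the subject. In Appendix 4 the last marks for AEs and for concomitant medications are in the early termination/safety follow-up column. The long-term follow-up (LTFU) column marks only time-to-next treatment and monthly HBV PCR. By footnote v, the PCR applies only to subjects who are anti-HBc positive or have a known history of HBV infection.

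**The concern.** The visit that is meant to capture new events can take place before the period for capturing them has ended. The plus side of the tolerance does no harm, because a visit on days 30 to 37 looks back over the whole period. The minus side leaves a stretch between the visit and day 30 in which no AE or concomitant-medication collection is scheduled.

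Characterizing safety is the only primary objective (Section 2.1). After day 30, Section 6.2.1 asks only for serious events or events of concern believed related to study drug. A new non-serious event between an early visit and day 30 falls within the reporting period, but whether anyone asks about it depends on when the site booked the visit. With 20 planned subjects, one subject is 1/20 = 5 percentage points of any AE incidence, so ascertainment should not turn on the booking date.

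**Working it through.** The protocol states no figure for this gap, so there is none to reproduce. The check is interval arithmetic on the stated windows and a reading of the Appendix 4 rows.

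**Inputs**
- Visit: day 30, tolerance ±7 days (synopsis, Sections 3.1 and 4.3, Appendix 4 footnote c).
- AE collection: to day 30, or to new anticancer therapy if earlier (Section 6.2.1).
- Concomitant medications: to day 30 (Section 4.1.4).
- Scheduled AE or concomitant-medication collection after the visit: none marked (Appendix 4).

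**Permitted visit days**
- Earliest: 30 − 7 = day 23. Latest: 30 + 7 = day 37.
- Number of permitted days: 37 − 23 + 1 = 15.

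**Gap for a visit on day v**
- Gap = max(0, 30 − v) days, for a subject who starts no new anticancer therapy by day 30.
- v = 23: 30 − 23 = 7 days (days 24 to 30), and 7/30 = 23% of the period. This is the worst case.
- v = 30 to 37: 0 days.

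**Average over all subjects, if visits fall evenly over days 23 to 37 (assumption)**
- Sum of gaps for days 23 to 29: 7 + 6 + 5 + 4 + 3 + 2 + 1 = 28 days. Days 30 to 37 add 0.
- Mean: 28/15 = 1.9 days, and 1.9/30 = 6% of the period.
- The protocol does not say how visits will be distributed. If they cluster at the nominal day 30 the mean is smaller; if sites tend to book early it is larger, with 7 days as the ceiling.
- If new anticancer therapy starts before day 30, AE reporting stops then and the AE gap is shorter or absent.

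**Does another passage close the gap?**
- Sections 3.8 and 4.4 mention continued follow-up for safety, but both refer for it to Section 4.3, which is the same visit.
- Appendix 4 footnote s, attached to the LTFU column, also names safety follow-up. It gives no interval, and the column has no AE or concomitant-medication mark.
- No scheduled collection of either therefore lies between an early visit and day 30.

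**The case against.** The strongest reply is that the reporting duty does not hang on the visit. Section 6.2.1 requires all AEs to day 30 without reference to it. Section 6.2.2 covers events that the subject volunteers or that come to light by other means, and Section 6.2.6 has events already found followed until resolved or stable, or until one of its listed end points such as new anticancer therapy. This stands. A reader might infer that events on days 24 to 30 go unreported, and the protocol does not support that. The most that can be said is that new events, mainly non-serious ones, might not be actively sought at a scheduled contact.

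A second reply is that footnote s keeps subjects on study for safety, so an LTFU contact could pick up late events. This stands in part: it could, but nothing fixes when such a contact takes place or that AEs are collected at it.

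A third is that a symmetric ±7-day tolerance is ordinary and that all four places agree on it. Both are true. The mismatch is with the fixed collection periods, not among the statements of the visit window.

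A reader might also extend the point to pregnancy and laboratory safety, since contraception (inclusion criterion 6) and the pregnancy reporting in Section 6.2.4 also run to 30 days. That extension fails. Section 6.2.4 goes by estimated date of conception and includes pregnancies identified after the study, whatever the visit date. A urine test on day 30 could not exclude a conception shortly before. A blood draw measures a single day, so moving it later does not cover days 24 to 30.

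**Conclusion.** The point holds as a minor mismatch in the timing of data collection. A compliant visit can leave up to 7 of the 30 post-dose days (23%) without a scheduled AE assessment or concomitant-medication collection. The 23% belongs to a day-23 visit and is not a typical loss; under the even-spread assumption the mean over all subjects is about 1.9 days (6%). Both figures are for subjects who start no new anticancer therapy before day 30.

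No numerical result in the protocol is wrong, and AEs arising on those days must still be reported. The reason to act is that ascertainment for the sole primary objective should not depend on the booking date.

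One separate inconsistency lies nearby: Section 3.7.9 asks female subjects to notify a pregnancy within 2 days after the last dose, while Section 6.2.4 covers conceptions up to 30 days after it. Those two passages need to be reconciled with each other and are not part of this point.

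**What to change.** Reconcile the visit window in the synopsis, Sections 3.1 and 4.3 and Appendix 4 footnote c with the 30-day periods in Sections 6.2.1 and 4.1.4, so that the last scheduled AE and concomitant-medication collection does not fall before those periods end. Either of two edits would do it:

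- remove the minus side of the tolerance in the four places; or
- keep the ±7 days and add to Section 4.3 and Appendix 4 a telephone collection of AEs and concomitant medications at day 30 whenever the visit was held earlier.

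The existing rule on new anticancer therapy stays as it is. The first edit adds no visit and costs sites some scheduling flexibility. The second keeps that flexibility and costs one short call per subject seen early. Neither touches dosing, treatment or stopping rules.

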4.4 TIME-TO-NEXT TREATMENT

Subjects who discontinue study therapy will continue on study for follow-up of safety ([Section 4.3](#)) and time-to-next DLBCL therapy unless they withdraw consent for further follow-up. Thus, all subjects receiving ≥ 1 dose of study drug will be followed during the immediate post-therapy and long-term follow-up assessments unless the subject withdraws consent for such follow-up to be conducted. The date the subject is withdrawn from the study and the reason for discontinuation will be recorded and also should be described on the appropriate electronic case report form (eCRF).

4.5 MISSED EVALUATIONS

Missed evaluations should be rescheduled and performed as close to the original scheduled date as possible. An exception is made when rescheduling becomes, in the

investigator's opinion, medically unnecessary or unsafe because it is too close in time to the next scheduled evaluation. In that case, the missed evaluation should be abandoned.

5.0 STATISTICAL METHODS OF ANALYSIS

5.1 GENERAL CONSIDERATIONS

This proof-of-concept study is designed to assess the safety, PK/PD, and activity of *acalabrutinib* 100 mg BID in subjects with relapsed/refractory de novo ABC DLBCL.

5.1.1 Response Assessment

Response assessments will be done by the investigators.

5.1.2 Safety Monitoring

The safety plan includes quarterly conference calls between Acerta and investigators to discuss study-specific issues including adverse events and serious adverse events.

5.2 DEFINITION OF ANALYSIS SETS

The following definitions will be used for the efficacy and safety analysis sets.

Safety analysis set: All enrolled subjects who receive ≥ 1 dose of study drug.

Per-protocol (PP) analysis set: All enrolled subjects who receive ≥ 1 dose of study drug, have sufficient baseline measurements, and undergo ≥ 1 assessment for the endpoint of interest (eg, response and PK/PD parameters) after treatment.

Intent-to-treat (ITT) population: All subjects who have enrolled in the protocol.

The safety analysis set will be used for evaluating the safety and efficacy, except duration of response, parameters in this study. The PP and ITT analysis sets will be analyzed for efficacy and PK/PD parameters in this study.

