3.4.3 Replacement of Subjects

Any subject who does not complete Cycle 2 may be replaced at the discretion of the study investigator and sponsor.

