4.1.20 Tumor Assessment

A pretreatment CT scan with contrast (unless contraindicated) is required of the chest, abdomen, and pelvis and any other disease sites (eg, neck) within 30 days before the first dose of study drug. A pretreatment positron-emission tomography (PET)/CT scan within 90 days before the first dose is also required. Information on extranodal involvement will also be recorded.

During treatment, CT scans with contrast (unless contraindicated) of the chest, abdomen, and pelvis and any other disease sites (eg, neck) will be done for tumor assessments at the end of Cycle 2 (± 7 days), Cycle 4 (± 7 days), and Cycle 6 (± 7 days); and then every 3 cycles (12 weeks, ± 7 days) thereafter or more frequently at investigator discretion. On-study tumor assessments will also be done by physical exam and laboratory results. Bone marrow and PET/CT are only required for confirmation of CR per clinical guidelines (see [Section 4.2](#)).

Note: For sites in Germany, radiologic tumor assessments will not include PET. Radiologic tumor assessments will be done at Screening and at the end of Cycle 2 (\pm 7 days) OR Cycle 4 (\pm 7 days) depending each on subjects' individual response; thereafter they will be done at investigator discretion. On-study tumor assessments will also be done by physical exam and laboratory results.

De-identified copies of all radiology results maybe requested by the sponsor.

Subjects should have radiographic tumor measurements done at the participating study center or an acceptable alternate imaging facility using an identical imaging protocol and similar equipment. The same imaging equipment should be used for all scans whenever possible. The same radiologist should be assigned to read all the scans for a given subject throughout the study.

In the event disease progression is suspected due to physical examination or laboratory test, a CT and PET/CT scan must be performed to confirm disease progression. There must be radiographically measurable disease at screening (\geq 1 lymph node $>$ 2.0 cm in the longest diameter). If the sole lesion lies within the field of prior radiotherapy, there must be evidence of disease progression in that lesion.

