5.5.4 Analysis of Efficacy Parameters

Response Rate

The individual and composite endpoints of response and progression will be determined. Tumor control will be documented at each assessment by response category (eg, CR, PR, SD, PD) as defined for each response parameter, date that response is first documented, and date of DLBCL disease progression.

Overall response rate will be defined as the proportion of subjects who achieve a CR or PR. Overall response rate will be calculated and the corresponding 97.5% one-sided confidence interval will be derived.

Duration of Response

The duration of response (DOR) defined as the interval from the first documentation of CR or PR to the earlier of the first documentation of definitive disease progression or death from any cause. Kaplan-Meier methods will be used to estimate event-free curves and corresponding quantiles (including the median). Data from surviving, nonprogressing subjects will be censored at the earliest of the time of initiation of anticancer treatment other than the study treatment or the last time that lack of definitive DLBCL progression was objectively documented. Data from subjects who have DLBCL progression or die after ≥ 2 consecutive missing tumor assessments will be censored at the last time before the missing assessments that lack of DLBCL progression was objectively documented.

Progression-free Survival

Progression-free survival (PFS) is defined as the interval from the start of acalabrutinib therapy to the earlier of the first documentation of objective DLBCL disease progression or death from any cause. Kaplan-Meier methods will be used to estimate the event-free curves and corresponding quantiles (including the median). Data from surviving, non-progressing subjects will be censored at the earliest of the time of initiation of anticancer treatment other than the study treatment or the last time that lack of DLBCL progression was objectively documented. Data from subjects who have DLBCL progression or die after ≥ 2 consecutive missing tumor assessments will be censored at the

last time prior to the missing assessments that lack of FL progression was objectively documented.

Time-to-Next Treatment

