6.2.2 Assessment of Adverse Events

Investigators will assess the occurrence of AEs and SAEs at all subject evaluation timepoints during the study. All AEs and SAEs whether volunteered by the subject, discovered by study personnel during questioning, or detected through physical examination, or other means will be recorded in the subject's medical record and on the AE eCRF and, when applicable, on an SAE/Product Compliant form.

Disease progression itself is not considered an AE; however, signs and symptoms of disease progression may be recorded as AEs or SAEs.

Symptomatic deterioration may occur in some subjects. Symptomatic deterioration is when progression is evident in the subject's clinical symptoms and the investigator may elect not to perform further disease assessments.

Each recorded AE or SAE will be described by its duration (ie, start and end dates), severity, regulatory seriousness criteria, if applicable, suspected relationship to the study drug (see following guidance), and any actions taken. The relationship of AEs to the study drug will be assessed by means of the question: 'Is there a reasonable possibility that the event may have been caused by the study drug?' Answer Yes or No.

See [Appendix 3](#) for more detail on assessing relationship.

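### Three unranked efficacy sets, one of which (PP) can drop early failures and inflate its ORR; separately, unscanned clinical progression is censored and biases PFS upward

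*Protocol*

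**What the plan says.** **Analysis sets.** Protocol Section 5.2 defines the safety set as "All enrolled subjects who receive ≥ 1 dose of study drug". PP adds two conditions: sufficient baseline data, and that the subject must "undergo ≥ 1 assessment for the endpoint of interest (eg, response and PK/PD parameters) after treatment". ITT is everyone enrolled. On use, the section says "The safety analysis set will be used for evaluating the safety and efficacy, except duration of response, parameters in this study", and then "The PP and ITT analysis sets will be analyzed for efficacy and PK/PD parameters in this study". ORR, PFS and time-to-next treatment are therefore each analysed in three sets, with no order among them.

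**Replacement.** Section 3.4.3: "Any subject who does not complete Cycle 2 may be replaced at the discretion of the study investigator and sponsor". That window closes about when the first on-treatment scan is due (end of Cycle 2, Section 4.1.20; Cycle 2 or Cycle 4 at sites in Germany).

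**Suspected progression.** Where examination or laboratory findings raise the suspicion, Section 4.1.20 says "a CT and PET/CT scan must be performed to confirm disease progression". Section 6.2.2, in text on symptomatic deterioration that Amendment 4 added, says that when progression shows in the clinical symptoms "the investigator may elect not to perform further disease assessments".

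**Events and censoring.** In Section 5.5.4 a PFS event is objective progression or death from any cause. The DOR paragraph states "Data from surviving, nonprogressing subjects will be censored at the earliest of the time of initiation of anticancer treatment other than the study treatment", or at the last objective documentation of no progression. The PFS paragraph has the same rule, and Section 5.3 is to the same effect. Progression or death after two or more consecutive missed tumor assessments is censored back to the last documentation before the gap.

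**The concern.** There are two separate problems.

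First, PP selects on something that happens after treatment starts. A subject who deteriorates or dies before any response assessment is not a responder, yet leaves the PP denominator. With three unranked results for each endpoint, the protocol does not say which one is the activity estimate of this proof-of-concept study, and the PP figure can only equal or exceed the all-dosed one.

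Second, a subject whose progression is clinically obvious but never imaged has no objective progression date. If alive, that subject is treated as progression-free up to the last documentation or the start of new therapy. Subjects are then censored because they are doing badly, which is informative censoring, and Kaplan-Meier reads too high. No choice of analysis set removes this. The same applies to DOR for a responder who later deteriorates without a scan.

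**Working it through.** **Inputs.** Planned N = 20 (Section 5.4), given without power or a hypothesis test, so there is no planned figure to reproduce. Scans fall at the ends of Cycles 2, 4 and 6 (Section 4.1.20); with 28-day cycles that is weeks 8, 16 and 24. The protocol gives no early-failure share, no median PFS and no share of clinical-only progressions. Those are assumptions, shown as ranges.

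**ORR.** Take n dosed, x responders and k failing with no response assessment, f = k/n. No unassessed subject is a responder, so

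- safety-set ORR = x/n
- PP ORR = x/(n − k) = (x/n) × 1/(1 − f)

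With x = 5, k = 5, n = 20: safety set 5/20 = 25% (exact 95% CI 8.7% to 49.1%); PP 5/15 = 33% (11.8% to 61.6%). The lower limits are also the 97.5% one-sided bounds that Section 5.5.4 asks for.

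With x = 8, where the safety set gives 8/20 = 40.0% (lower bound 19.1%) whatever k is:

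| k | PP ORR | PP lower bound |
|---|---|---|
| 2 | 8/18 = 44.4% | 21.5% |
| 4 | 8/16 = 50.0% | 24.7% |
| 6 | 8/14 = 57.1% | 28.9% |

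Scaled to the 41% ORR that Section 1.2 cites for ibrutinib in ABC DLBCL (used here only as an illustrative true rate), PP would read 45.6%, 51.2% or 58.6% at f = 10%, 20% or 30%.

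Replacement does not itself change any set. If 2, 4 or 6 such subjects are replaced until PP again holds 20 with 8 responders, PP reads 8/20 = 40.0%, while all-dosed reads 8/22 = 36.4%, 8/24 = 33.3% or 8/26 = 30.8%.

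**PFS, the passages side by side.** Section 4.1.20 demands a scan; Section 6.2.2 permits none. Section 5.5.4 accepts only objective progression or death as an event and has no rule for symptomatic deterioration. The Appendix 4 schedule marks no tumor assessment at early termination/safety follow-up or in long-term follow-up, so a skipped scan is not recovered later.

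**PFS, size.** Assume exponential PFS with median 3 months (13.04 weeks) and scans every 8 weeks. Survival through one interval is 2^(−8/13.04) = 0.654, so 0.346 fail. True 24-week PFS = 0.654³ = 28%.

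If a share p of failures is clinical only and censored at the preceding scan, those subjects leave the risk set. The interval factor becomes 0.654/(1 − 0.346p), and 24-week PFS is its cube:

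- p = 10%: (0.654/0.9654)³ = 31%
- p = 20%: (0.654/0.9308)³ = 35%
- p = 30%: (0.654/0.8962)³ = 39%

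Simulation under the same assumptions gives 31.1%, 34.6% and 38.8%. These are upper limits for the stated p, because no censored subject is allowed to die later and count as an event.

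As a second illustration, confined to failures before week 8: with an assumed true median of 12 weeks (37% fail by then), censoring 25% or 50% of those failures at day 1 moves the Kaplan-Meier median to 13.7 or 15.6 weeks.

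**The case against.** A reader might infer that ORR and PFS as a whole are biased because every early failure is removed, replaced or censored. The documents do not support that, for four reasons.

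- **ORR outside PP.** Section 5.2 also requires efficacy in the safety set and in ITT. Both keep early and replaced subjects in the denominator, and an unassessed subject there is already not a responder.
- **Deaths.** Death from any cause is a PFS event. A death before the first scan is counted in the safety and ITT sets; only death after two or more consecutive missed assessments is censored back.
- **DOR.** It starts at the first CR or PR, so a subject who fails before any response never enters it. Only later unscanned deterioration in a responder matters.
- **Meaning of assessment.** PP asks for an assessment, not a scan. Section 4.1.20 says on-study tumor assessment is also done by physical examination and laboratory results. Some early failures may therefore stay in PP, and f could be small.

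These points stand, and they limit the claim to PP ORR and to surviving, unscanned progressions.

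It can also be said that the choice of main set may be made in the SAP, which is not at hand; that safety is the primary objective and no hypothesis is tested; and that a 3-point shift (p = 10%) is small beside a standard error of √(0.28 × 0.72/20), about 10 points. All are fair and keep the point modest. They do not remove the contradiction between Sections 4.1.20 and 6.2.2, or the equal standing that Section 5.2 gives PP.

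Finally, efficacy rests on the Lugano criteria, and Table 4-2 has no category for symptomatic deterioration. Making it a main PFS event would bring subjective judgment into an open-label study. That is a good reason to keep it to a sensitivity analysis.

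**Conclusion.** The point holds in two limited parts.

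1. PP ORR is inflated by 1/(1 − f), where f is the share of dosed subjects failing without a response assessment. Safety-set and ITT ORR are not. The defect is that the inflated figure stands beside the others unranked.
2. Sections 4.1.20 and 6.2.2 contradict each other, and a surviving subject with unscanned clinical progression is censored. That biases PFS upward in every set, and DOR for responders who later deteriorate unscanned. The size is at most 31%, 35% or 39% against a true 28% at 24 weeks for p = 10%, 20% or 30%, resting on an assumed 3-month exponential median and no later deaths counted. If Section 4.1.20 is followed in practice, p is near zero and so is the bias.

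A smaller matter of fit: Section 3.4.4 dates enrollment before treatment, so ITT may hold undosed subjects. They have no start date for PFS or time-to-next treatment, both of which run from the start of acalabrutinib, and no on-drug PK/PD data.

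**What to change.** - **Section 5.2:** name the all-dosed (safety) set as the main set for ORR, PFS and time-to-next treatment. State that replaced dosed subjects stay in the ORR denominator and that anyone not evaluable counts as a non-responder. Label PP as supportive only. Do not use ITT for PFS, time-to-next treatment or PK/PD.
- **Section 5.5.4:** keep the Lugano-based PFS and DOR as main. Add a prespecified sensitivity analysis that counts documented symptomatic deterioration, or the start of new anticancer therapy, as an event on its recorded date.
- **Sections 4.1.20 and 6.2.2:** reconcile them, so that one rule governs imaging when progression is suspected or clinically evident.

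The cost is wording in these sections and in the SAP, plus one extra analysis each for PFS and DOR. New data collection should not be needed: Section 4.1.21 already has suspected progression reported electronically within 24 hours, and next-therapy dates are collected for time-to-next treatment. The downside is slightly more analysis and somewhat less favourable activity estimates.
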